1. Women who are pregnant, breast feeding, or planning a pregnancy over the duration of the study period. Women must agree to use an adequate form of contraception or abstain from sexual intercourse for the duration and for at least one month after the end of the study.
2. Current treatment of cancer or diagnosed with cancer (except basal or squamous-cell carcinoma not treated with chemotherapy and/or radiation) in the past 6 months.
3. Poorly controlled, brittle, or pump-dependent Type I diabetes.
4. Current peptic ulcer bleeding.
5. Allergy to adhesive tape.
6. Skin problems or sensitivities. Eligibility will be evaluated on a case-by-case basis by the Study Physician.
7. Active hepatitis or poorly controlled kidney and/or liver disease.
8. Uncontrolled hypertension (systolic blood pressure [SBP] greater than 159 and/or diastolic blood pressure [DBP] greater than 99; see Blood Pressure Procedures under Screening/Covariates).
9. History of abnormal heart rhythms, tachycardia, and/or cardiovascular disease (e.g. stroke, angina, heart attack) may result in ineligibility. These conditions will be evaluated on a case-by-case basis by the Study Physician.
10. History of epilepsy or seizures. Eligibility will be evaluated on a case-by-case basis by the Study Physician.
11. Serious or unstable disease within the past 6 months. Notable diseases will be evaluated on a case-by-case basis by the Principal Investigator and/or the Study Physician.
12. Any impairment including, but not limited to, visual, physical, and/or neurological impairments preventing proper completion of the study procedures. Notable impairments will be evaluated on a case-by-case basis by the Principal Investigator and/or the Study Physician.
13. Low or borderline intellectual functioning – determined by receiving a score of less than 75 on the Shipley Institute of Living Scale (SILS), which correlates with the Wechsler Adult Intelligence Scale-Revised (WAIS-R) Estimated IQ Test.
14. Applicable food allergies or disorders:
 - Galactosemia ^a
 - Notable milk allergy (lactose intolerant participants may proceed unless they experience severe symptoms) ^b
 - Notable soy allergy ^c
 - Peanut allergy ^d

^{a,b,c} Boost® Original Very Vanilla Nutritional Shake: Contains milk and soy ingredients. Suitable for Lactose Intolerance.

^{a,b,c,d} M&M's® (Milk Chocolate): Contains milk and soy ingredients (MAY CONTAIN PEANUTS)

Lay's® Classic Potato Chips (Gluten Free): Potatoes, vegetable oil, and salt

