6.2.12 Follow-Up Visits 1 and 2 (Week 12 and Week 26)

During Follow-Up Visits 1 and 2 (Duration: ~30 minutes) participants will:

1. Perform a CO breath assessment or provide a urine sample for a cotinine assessment, answer combustible marijuana items, and complete a concomitant medication review.
2. Provide daily smoking rate (timeline follow back [TLFB]).
3. Have weight measured.
4. Complete paper and pencil questionnaires:
 - Adverse Events Form (Open-Ended AEs)
 - Physical Activity (PAR)
5. If a participant reports not smoking (not even a puff of a cigarette) for at least the 7 days prior to the Follow-Up Visit without the aid of NRT, the participant will be asked to provide a 5ml saliva sample used to assess cotinine levels and verify abstinence from smoking.
6. Confirm the 24-hour dietary recall (Week 12 [#4] and Week 26 [#5]) schedule.

6.2.13 fMRI Scan Visits 1 & 2 (~Week -2 and ~Week 7-8)

Participants who are both eligible and elect to participate in the neuroimaging sub-study will complete two neuroimaging sessions: Scan 1 will occur prior to the Baseline Visit (~week -2) and Scan 2 will occur during the final week of nicotine patch therapy (~week 7-8). Prior to each scan, participants will be instructed to fast overnight (beginning at ~10pm) until after the

CONFIDENTIAL

This material is the property of the University of Pennsylvania. Do not disclose or use except as authorized in writing by the study sponsor

completion of their fMRI scanning visit the following day. The fast period does not include a Boost® Nutritional Drink (Vanilla) that will be provided during the scanning visit to standardize prior food intake and remove deprivation to increase sensitivity to changes in food reward. Since participants are asked to fast overnight, all scanning sessions will be scheduled to occur in the morning. However, a scan may be completed in the afternoon at the discretion of the Principal Investigator due to extenuating circumstances. Additionally, participants will be instructed not to consume caffeine for 4 hours prior to the beginning of the visit in order to standardize satiety. Including the 1-hour fMRI scan, scanning visits are expected to last ~3 hours in duration. If a scanner hardware/software malfunction occurs and data is unable to be collected, an fMRI scan(s) may be rescheduled at the discretion of the Principal Investigator.

At both scanning visits participants will:

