Reinforcement/Choice task. Participants will be expected to demonstrate an understanding of the tasks and the response device prior to the fMRI scan.

11. Be provided with a Boost® Nutritional Drink and water.
12. Be escorted to the imaging facility at either the Hospital of the University of Pennsylvania or the Stellar Chance building for the brain-scanning portion of the session.
13. **SCAN 1 ONLY:** Participants will smoke one of their own cigarettes (~30 min. before initiating fMRI) in a designated smoking area outside of the building where the fMRI scanner is located in order to standardize the timing of cigarette exposure for all participants.
14. **SCAN 2 ONLY:** Participants will be instructed to remove their TN patch prior to entering the MRI environment. Participants will be provided with a loose, sealed 7mg (NicoDerm® CQ® - Clear) patch to reapply after exiting the MRI environment.
15. Undergo a 1-hour fMRI scan adhering to the procedures and Table 1 below:

Scanning Protocol/Data Acquisition: MRI is performed in a 1-hour session, which, in our experience, participants tolerate easily without discomfort or excessive motion. Prior to entering the scanning area, an approved MRI Technician or MRI User will review the participant's magnet safety form and will confirm that the participant has removed all metal and/or objects containing magnetic strips from their persons. Once the participant is approved to enter the scanning area, the participant will be placed supine in the scanner, wearing earplugs to muffle noise, and fitted with adjustable foam cushions to limit head motion. If a participant requires corrective lenses for vision, but does not have contact lenses, a set of plastic glasses that are approved for use in an MRI scanner will be provided to him/her. Participants will be provided with an emergency squeeze ball, so that they may interrupt the scan and/or be removed from the scanner if necessary. Head fixation will be assured through a foam-rubber device mounted on the headcoil.

Image acquisition is performed on a 3T Siemens Tim-Trio scanner with a FDA approved head coil. A T1-weighted multi-echo magnetization-prepared, rapid acquisition gradient echo (MPRAGE) structural image is acquired using standard parameters at 1mm resolution. This MPRAGE is used for functional image co-registration and transformation into standard template space. Resting BOLD fMRI will be obtained followed by the three task paradigms.

TABLE 1: fMRI Session	

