Food Cue Reactivity: The task will present (5 sec) 20 pictures of food rated (at Intake) as most appetizing and 20 pictures of food rated (at Intake) least appetizing, and 20 pictures of a water glass. Participants will be instructed to imagine tasting and eating the pictured food for as long as the food is presented. Order of presentation is randomized and the task consists of 60 events separated by an inter-stimuli interval (fixation point) ranging from 2-11 sec (mean 5.5 sec). As a secondary measure, food craving will be assessed prior to and after completion of the scan. The food craving assessment is the 3-item “desire” subscale of the reliable and valid state version of the Food Craving Questionnaire (FCQ-S). Total task time: ~10 minutes.

Food Reinforcement/Choice: Participants choose between a standard low effort monetary reward and either (on separate trials) a food or monetary reward of higher value and effort. Each trial presents a choice between a standard reward (27 button clicks for \$0.25) or exerting greater effort to earn a larger reward. On half of the trials, larger rewards will be \$0.50 (2 x standard value). In the remaining trials the larger reward will be double the calibrated snack portion (e.g., 20 M&Ms). Effort for more valuable rewards will vary from 27 to 775 responses in 25 log10 steps. Pairs of visual stimuli depicting the two options appear for 4.5 sec followed by a 3-14 sec inter-trial interval. Each pairing is presented twice making 50 trials for each class. Left/right position of stimuli is randomized, as is trial type (monetary vs. food; effort levels). To increase motivation to choose food and monetary reward, participants are told they will complete the work and receive the outcome of 4 randomly selected food and monetary (maximum \$2.00) trials. Total task time: ~15 minutes.

Working Memory: We will use a 12-minute visual N-back task validated for fMRI studies of smokers. A total of 20 fractals (target-foil ratio 1:3) are presented for each condition (i.e., 0-back, 2-back, 3-back), and each condition (60 sec block) is repeated 3 times in pseudo-random block design experiment. Each fractal is displayed for 500ms followed by 2500ms inter stimuli interval. Total task time: ~12 minutes.

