16. When all scans are completed, participants will be removed from the MRI scanner and be asked to complete a brief ~5-minute “work” task (i.e. clicking on a target a certain amount of times) based on their selections during the in-scanner Food Reinforcement/Choice task on a laptop computer.
17. Participants will receive the appropriate reward(s) (food and/or monetary) per the post-scan work task, as well as receive compensation for time and travel per the study compensation schedule. At the end of the session, participants will be escorted to the exit of the imaging facility where s/he will be free to leave.

6.3 ***Microbiome Sub-Study***

Participants who are both eligible and elect to participate in the microbiome sub-study will be instructed to collect and return stool samples to the Center at **Week -2 (Baseline Visit)**, **Week 4 (Mid-Tx 3 Visit)**, and **Week 8 (End of Treatment Visit after completing TN treatment)**. Participants will be asked about their consumption of yogurt, probiotics, and prebiotics at **the Baseline Visit, Mid-Tx 3 Visit, and End of Treatment Visit**. Participants will be asked to answer a few questions regarding their antibiotic use over the past 6 months at the **Baseline Visit** as well.

Participants will receive a stool sample collection kit and detailed instructions (written and verbal) about how to complete the collection of their stool sample at the in-Center visit prior to the visit when which they are scheduled to return their sample. Ideally, stool samples will be

CONFIDENTIAL

This material is the property of the University of Pennsylvania. Do not disclose or use except as authorized in writing by the study sponsor

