Food Allergies: Participants will be provided with nutritional shakes and potato chips or milk chocolate and as part of their participation in this research trial. The risk of a participant experiencing an allergic reaction to any of the ingredients in these commercially available food products will be mitigated by prospectively excluding those with the applicable food allergies. In addition, the research staff will reconfirm that the participant doesn't have any of the applicable food allergies prior to distribution of the aforementioned food products at the Baseline Visit.

Psychological Distress: Participants may experience emotional distress during smoking cessation counseling and assessments from discussing feelings and attitudes about smoking or from learning about the risks from smoking. These events happen very rarely and in almost all cases are short-lived and of low intensity, lasting for 1-2 weeks. Study personnel will be alerted to expect this from a small number of subjects and will be trained to make referrals for mental health services as needed. Personnel will be trained to query for adverse emotional reactions during counseling and assessments and will be trained to deal with such reactions and to provide additional referrals if needed.

Urine and Saliva Sample Collection: Participants may experience mild discomfort from providing urine or saliva samples. All samples will be collected by trained member of the research staff.

Email Communications: In this research study participants may prefer to receive appointment reminders via email or submit questions related participation via email. Email is not a secure means of communication. Email messages travel across the Internet passing through multiple

CONFIDENTIAL

This material is the property of the University of Pennsylvania. Do not disclose or use except as authorized in writing by the study sponsor

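### For neuroimaging participants, the secondary food-allergy recheck is placed at Baseline, after Scan 1 has already provided the shake and any snack earned

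*Combined protocol and SAP*

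**What the plan says.** Section 7.1 (Food Allergies) describes two layers of protection. The first is prospective exclusion of people with the relevant allergies. The second, introduced as an addition, is a reconfirmation by staff that the participant has none of the "applicable food allergies prior to distribution of the aforementioned food products at the Baseline Visit". No other visit is named for it.

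Section 4.6 (Medical, item 14) lists the allergies and the products behind them. The Boost entry reads "Nutritional Shake: Contains milk and soy ingredients". The sweet snack is described as "M&M's® (Milk Chocolate): Contains milk and soy ingredients (MAY CONTAIN PEANUTS". The chips are listed with potatoes, vegetable oil and salt only.

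Section 6.2.13 covers the scan visits. On order it says "Scan 1 will occur prior to the Baseline Visit (~week -2", and Table 2 places the Scan 1 column ahead of Baseline. Among the steps for both scan visits, step 11 is "Be provided with a Boost® Nutritional Drink and water", and step 17 begins "Participants will receive the appropriate reward(s) (food and/or monetary) per the post-scan work task". The task description in the same section says "participants are told they will complete the work and receive the outcome of 4 randomly selected food and monetary" trials.

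**The concern.** Tying a recheck to the handing out of food at Baseline protects a participant at first exposure only if no study food has been given before then. That is so for parent-study participants who are not scanned. It is not so for those in the neuroimaging sub-study, who are given the shake at an earlier visit.

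A second check exists to catch an allergy that was overlooked or not disclosed at eligibility review. It does that job only if it comes before the food. Section 7.1 also sets out for the ethics board how each risk is handled, so the description should hold for every group of participants it covers. For the scanned group, one of the two layers described is not in place at first exposure.

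**Working it through.** No arithmetic applies; the point is one of sequence. These are the relevant statements in visit order.

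1. **Intake (about week -3), section 6.2.2.** A Medical History Form led by staff reviews the exclusions, which include item 14 of section 4.6. Participants rate food pictures and choose chips or M&M's for later tasks. No step gives them food.
2. **Scan 1 (about week -2, before Baseline), section 6.2.13.** Step 11 gives the shake, with no condition attached. Step 17 gives whatever was earned in the post-scan work task, and step 10 identifies the food reward as the preferred snack, chips or M&M's.
3. **Baseline (about week -2), section 6.2.3.** The shake is given before the laboratory tasks, and the food reinforcement task can yield a snack. Section 7.1 places the reconfirmation at this visit.

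The two paths are therefore:

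| Participant | Order as written |
|---|---|
| Parent study only | Intake exclusion → Baseline reconfirmation → first food |
| Neuroimaging sub-study | Intake exclusion → Scan 1 food → Baseline reconfirmation |

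**Is the recheck stated elsewhere for Scan 1?** Section 6.2.13 numbers 17 steps. The checks among them are a urine drug screen, pregnancy test, breath alcohol, CO with marijuana items and medication review, recent smoking, weight and a magnet safety form, with patch adherence and side-effect forms at Scan 2 only. None is a food-allergy question. The fMRI exclusion list in section 4.6 does not mention food allergy either. Scan 2 raises no ordering problem, because it falls after Baseline.

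**Which products are involved?** The shake, with milk and soy, goes to everyone scanned. The snack is conditional. A participant may earn only money, and one who chose chips receives a product listed without milk, soy or peanut. Possible peanut exposure at Scan 1 therefore arises only for someone who chose M&M's and earned them.

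**How many people?** Section 4.3 plans to enrol about 75 into the sub-study to obtain about 50 completers with usable data. The 75 is planned enrolment, not a count of Scan 1 attendances. It is the number of people for whom the order is reversed, not the number at risk of a reaction.

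**The case against.** The strongest reply is that the main protection is untouched. Section 7.1 credits exclusion with mitigating the risk and offers the reconfirmation only as an extra. Exclusion is reviewed about a week before Scan 1. Section 10.3.2 adds document review before Intake, real-time eligibility review at Intake and a signed Final Eligibility Checklist, and section 10.3.3 adds a separate checklist for the sub-study. All of this stands. A reader might infer that scanned participants receive food without any allergy screening, or that the risk section relies on the recheck alone. The documents support neither reading.

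A second reply is that the visit lists are not a full record of this check. The Baseline list in section 6.2.3 omits it too, although section 7.1 promises it there, and section 10.3.3 refers to checklists at every time point that are not reproduced. This also stands, within limits. It means that one cannot say the question is never asked at Scan 1, only that the protocol does not state it there.

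A third reply is that the sections do not strictly conflict, since staff could follow both as written. That is correct. But following both puts the second check after the first food in this group, and that is the defect.

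Finally, section 3.2 lets scan timing vary at the investigator's discretion, and section 3.5 expected the sub-study to finish by about April 2019, while section 6.2.11 refers to visits on or after 3/30/2020. The stated default order is still Scan 1 first. The dates do bear on how much practical use a correction has now.

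**Conclusion.** The point holds in a limited form. For neuroimaging participants, the secondary allergy reconfirmation in section 7.1 is timed after their first study food: the shake for all of them, and a snack for those who earn one. The primary safeguard, exclusion reviewed at Intake, comes before that food.

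The group concerned is about 75 planned enrolees. It would be tempting to say that the whole group is put at risk, but the documents do not support this. All of them lack a stated repeat question before first exposure, but only someone whose allergy was missed or not disclosed at Intake could be harmed by that. The documents give no rate for such misses, so no expected number of events can be stated.

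The conclusion assumes that scans follow the default order and that no unseen checklist already places the question at Scan 1. Randomisation, endpoints, power and analysis are not affected. It is a participant-safety inconsistency worth correcting because the correction is nearly free, and its practical value depends on whether scanning continues.

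**What to change.** If scanning is still under way, reconcile the Food Allergies paragraph of section 7.1 with section 6.2.13, so that the stated timing of the reconfirmation agrees with the stated order in which sub-study participants receive food. Reconcile it also with the Baseline steps in section 6.2.3, where the promised check is not listed. How the check is arranged clinically is for the investigator and Study Physician to settle; the request is only that the sections agree. If a visit checklist already covers the question, the protocol text should say so.

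The cost is about one sentence in section 7.1 and matching entries in the visit lists, with whatever ethics-board submission a wording amendment needs. The question is already part of the protocol, so no new assessment is required. If scanning has finished, no procedural change is needed.

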7.2 Potential Study Benefits

Participants who enroll in this trial will benefit from the knowledge that they are contributing in an important way to potentially furthering scientific knowledge concerning ways to improve treatment for smokers, and prevent PCWG. Weight gain can precipitate smoking relapse and contribute to other health issues. All eligible smokers will receive TN and behavioral counseling and may quit smoking and learn skills to stay quit as a result of participating.

7.3 Risk/Benefit Assessment

There is minimal risk for serious adverse events by enrolling in this research study. The treatments and procedures used in this study have been shown to be relatively safe. Numerous clinical trials have demonstrated the safety and efficacy of transdermal nicotine and behavioral counseling for nicotine dependence. Research staff will monitor subjects closely during their participation. Thus, the risk to benefit ratio for this project is perceived to be low and justifies its implementation.

8 Safety and Adverse Events

8.1 Definitions

Unanticipated Problems Involving Risk to Subjects or Others:

Any incident, experience, or outcome that meets all of the following criteria:

CONFIDENTIAL

This material is the property of the University of Pennsylvania. Do not disclose or use except as authorized in writing by the study sponsor

- Unexpected in nature, severity, or frequency (i.e. not described in study-related documents such as the IRB-approved protocol or consent form, the investigators brochure, etc.)
- Related or possibly related to participation in the research (i.e. possibly related means there is a reasonable possibility that the incident, experience, or outcome may have been caused by the procedures involved in the research)
- Suggests that the research places subjects or others at greater risk of harm (including physical, psychological, economic, or social harm).

Adverse Event:

An **adverse event** (AE) is any symptom, sign, illness or experience that develops or worsens in severity during the course of the study (regardless if TN related). Intercurrent illnesses or injuries should be regarded as adverse events. Abnormal results of diagnostic procedures are considered to be adverse events if the abnormality:

- results in study withdrawal
- is associated with a serious adverse event
- is associated with clinical signs or symptoms
- leads to additional treatment or to further diagnostic tests
- is considered by the investigator to be of clinical significance

Serious Adverse Event:

Adverse events are classified as serious or non-serious. A **serious adverse event** (SAE) is any AE that is:

- fatal
- life-threatening
- requires or prolongs hospital stay
- results in persistent or significant disability or incapacity
- a congenital anomaly or birth defect
- an important medical event

Important medical events are those that may not be immediately life threatening, but are clearly of major clinical significance. They may jeopardize the subject, and may require intervention to prevent one of the other serious outcomes noted above. For example, drug overdose or abuse, a seizure that did not result in in-patient hospitalization, or intensive treatment of bronchospasm in an emergency department would typically be considered serious.

All adverse events that do not meet any of the criteria for serious should be regarded as **non-serious adverse events**.

Adverse Event Reporting Period:

The study period during which AEs/SAEs will be reported is from the initiation of any study procedures until the end of the study. Any event(s) that the subject, or the subject's personal physician, believes might reasonably be related to participation in the study after the final time point will be assessed and reported as appropriate.

Preexisting Condition:

A preexisting condition is one that is present at the start of the study. A preexisting condition should be recorded as an adverse event if the frequency, intensity, or the character of the condition worsens during the study period.

Post-study Adverse Event:

CONFIDENTIAL

This material is the property of the University of Pennsylvania. Do not disclose or use except as authorized in writing by the study sponsor

All unresolved adverse events should be followed by the investigator until the events are resolved, the subject is lost to follow-up, or the adverse event is otherwise explained. At the last scheduled visit, the investigator should instruct each subject to report any subsequent event(s) that the subject, or the subject's personal physician, believes might reasonably be related to participation in this study.

Hospitalization, Prolonged Hospitalization or Surgery:

Any AE that results in hospitalization or prolonged hospitalization should be documented and reported as a SAE unless specifically instructed otherwise in this protocol. Any condition responsible for surgery should be documented as an AE if the condition meets the criteria for an AE.

Neither the condition, hospitalization, prolonged hospitalization, nor surgery are reported as an adverse event in the following circumstances:

- Hospitalization or prolonged hospitalization for diagnostic or elective surgical procedures for a preexisting condition. Surgery should **not** be reported as an outcome of an adverse event if the purpose of the surgery was elective or diagnostic and the outcome was uneventful.
- Hospitalization or prolonged hospitalization required to allow efficacy measurement for the study.
- Hospitalization or prolonged hospitalization for therapy of the target disease of the study, unless it is a worsening or increase in frequency of hospital admissions as judged by the clinical investigator.

